5.1 PRIMARY ENDPOINT

The primary efficacy endpoint is change from baseline in EASI Score at Week 16.

The absolute and percent change from baseline will be analysed as well as the absolute values at visits.

The EASI total score assesses the extent of disease (area affected) at four body regions: head, trunk, upper limb, and lower limb for which the following scoring will be used:

% involvement	0	1 to <10%	10 to <30%	30 to <50%	50 to <70%	70 to <90%	90 to 100%
Region score	0	1	2	3	4	5	6

The severity of each of the four clinical signs: erythema, induration/papulation, excoriation, and lichenification using the following severity scale for each body region:

- 0 for “None”
- 0.5 for “None to Mild”
- 1 for “Mild”
- 1.5 for “Mild to Moderate”
- 2 for “Moderate”
- 2.5 for “Moderate to Severe”
- 3 for “Severe”

The following formula will be used to derive the EASI Total Score:

$$\begin{aligned}\text{EASI Total Score} = & (\text{Erythema}_{\text{Head}} + \text{Edema/papulation}_{\text{Head}} + \text{Excoriation}_{\text{Head}} + \\ & \text{Lichenification}_{\text{Head}}) \times (\text{Head}_{\text{Region Score}}) \times 0.1 + \\ & (\text{Erythema}_{\text{Trunk}} + \text{Edema/papulation}_{\text{Trunk}} + \text{Excoriation}_{\text{Trunk}} + \\ & \text{Lichenification}_{\text{Trunk}}) \times (\text{Trunk}_{\text{Region Score}}) \times 0.3 + \\ & (\text{Erythema}_{\text{Upper limb}} + \text{Edema/papulation}_{\text{Upper limb}} + \text{Excoriation}_{\text{Upper limb}} + \\ & \text{Lichenification}_{\text{Upper limb}}) \times (\text{Upper limb}_{\text{Region Score}}) \times 0.2 + \\ & (\text{Erythema}_{\text{Lower limb}} + \text{Edema/papulation}_{\text{Lower limb}} + \text{Excoriation}_{\text{Lower limb}} + \\ & \text{Lichenification}_{\text{Lower limb}}) \times (\text{Lower limb}_{\text{Region Score}}) \times 0.4\end{aligned}$$

5.2 SECONDARY ENDPOINTS

5.2.1 Key secondary endpoint

Not applicable.

5.2.2 Secondary endpoints

The secondary endpoints are listed below.

- Drug-related Adverse Events (AEs)

Numbers and percentages of patients with drug-related AEs will be presented.

- Change from baseline in EASI Score at Week 4

The absolute and percent change from baseline as well as the absolute values at visits will be analysed.

- EASI50/75 responders at Week 4 and 16

Numbers and percentages will be analysed.

Achievement of Decrease in EASI \geq xx% (EASIxx)

Achieving a response of xx% or larger decrease from baseline in EASI score is denoted as EASIxx. The EASIxx represents a binary variable with values of 0 (= non-response) or 1 (=response).

It is calculated based on the following approach (with xx taking a value of 50 or 75):

$$\text{If } \left\{ \frac{\text{EASI(BL)} - \text{EASI(current)}}{\text{EASI(BL)}} \times 100 \right\} \geq xx \text{ then EASIxx}=1,$$

else EASIxx = 0.

- Change from baseline in SCORing of Atopic Dermatitis (SCORAD) at Week 4 and 16

The absolute and percent change from baseline as well as the absolute values at visits will be analysed.

The SCORAD consists of three elements: extent of disease, intensity of disease, and subjective symptoms (Pruritus and Sleep Loss). It sums up to a maximum of 103 points. Two of the SCORAD items are subjective symptoms (C) assessed on Visual Analog Scales (VAS) from 0 to 10: Pruritus VAS and Sleep Loss VAS.

The following formula will be used to calculate the SCORAD element assessing the Extent of the disease:

$$\text{Extent Score}(A) = (\text{Face}_{\text{Front}} \times 4.5 + \text{Upper_Limbs}_{\text{Front}} \times 9 + \text{Trunk}_{\text{Front}} \times 18 + \text{Lower_limbs}_{\text{Front}} \times 18 + \text{Genitals}_{\text{Front}} \times 1 + \text{Head}_{\text{Back}} \times 4.5 + \text{Upper_limbs}_{\text{Back}} \times 9 + \text{Trunk}_{\text{Back}} \times 18 + \text{Lower_limbs}_{\text{Back}} \times 18) / 100$$

In the SCORAD element assessing the Intensity of the disease the following scoring will be used:

- 0 for "Absence"
- 1 for "Mild"
- 2 for "Moderate"
- 3 for "Severe"

The SCORAD Intensity score element will be derived using the formula below:

$$\text{Intensity Score}(B) = (\text{Erythema_Score} + \text{Edema/Papulation_Score} + \text{Oozing/crusts_Score} + \text{Excoriations_Score} + \text{Lichenification_Score} + \text{Dryness_Score})$$

For the SCORAD element subjective symptoms the following formula will be used:

$$\text{Subjective symptoms}(C) = \text{Pruritus_VAS} + \text{Sleep_Loss_VAS}$$

The following formula will be used to calculate the SCORAD Total Score:

$$\text{SCORAD Total Score} = (A/5) + (B \times 7/2) + C$$

- Patients achieving at least a 2-grade reduction from baseline to clear (0) or almost clear (1) in the Investigator's Global Assessment (IGA) at Week 4 and 16

Numbers and percentages will be analysed.

IGA score allows investigators to assess the overall disease severity at one given time point. It is a 5-point scale with: 0 = clear, 1 = almost clear, 2 = mild, 3 = moderate, and 4 = severe. The overall IGA score includes the assessment of erythema, induration/papulation, lichenification, and oozing/crusting. For the first three sections the following scale will be used:

[figure not shown]
- “None”
- “Barely Perceptible” (“Minimal” for lichenification)
- “Slight but Definite”
- “Clearly Perceptible”
- “Marked”

[figure not shown]
For oozing/crusting the available answers are “None” or “Present.”

Following instructions will be used to derive the **IGA Score**:

- IGA Score = 0 if the answers in all sections are “None”.
- IGA Score = 1 if any of the following occurred: (erythema is barely perceptible OR induration/papulation is barely perceptible OR lichenification is minimal) AND no oozing/crusting is observed.
- IGA Score = 2 if any of the following occurred: (erythema is slight but definite (pink) OR induration/papulation is slight but definite OR lichenification is slight but definite), AND no oozing/crusting is observed.
- IGA Score = 3 if any of the following occurred: erythema is clearly perceptible (dull red) OR induration/papulation is clearly perceptible OR lichenification is clearly perceptible OR oozing/crusting is present.
- IGA Score = 4 if any of the following occurred: erythema is marked (deep or bright red) OR induration/papulation is marked OR lichenification is marked.

[figure not shown]
Note: For IGA score of 4, the oozing/crusting may be present.

[figure not shown]

Safety will be assessed based on:

- Adverse events
- Serious adverse events (SAEs)

6. GENERAL ANALYSIS DEFINITIONS

6.1 TREATMENTS

For basic study information on the treatment to be administered, assignment to treatment, and selection of dose, cf. Section 4 of the CTP.

In the blinded treatment phase, all patients will receive either intravenous doses of 600mg of BI 655130 solution for infusion (at weeks 0, 4, 8, and 12), or Placebo.

At Week 16, all patients will be evaluated with the EASI Score. Non-responders (EASI < 75) will be re-allocated to receive BI open label trial drug from Week 16 through Week 28; they will be followed until Week 44. Responders (EASI >= 75) will be re-assigned to receive no further trial treatment but will be expected to come to all visits up to Week 28, when EOS visit is planned.

The following trial periods/phases are defined:

Table 6.1: Flow chart of trial period/phases

Trial phase	Description	Start (included)	End (excluded)
Screening phase	Screening	Date of informed consent	Date of start of first infusion of study drug (day 1).
Blinded Treatment phase	Randomised On-treatment period	Date of start of infusion of first study drug (Day 1)	Week 16 visit date + 1 day
Open label Treatment phase ¹	Re-allocation period (Either open label BI655130 or No treatment)	Week 16 visit date + 1 day	Date of EoS Participation visit + 1 day

Dates are defined individually per patient. If more than one date is associated with a specific visit, measurements associated with a specific date are assigned to a study analysis phase according to the rules specified in the table. An analysis phase will not extend beyond the start date of the following phase.

¹ Non-responders (i.e. EASI<75) at Week 16 will be re-allocated to BI655130 600mg IV open label and will continue in the trial until Week 44. Responders (EASI>=75) at Week 16 will be re-allocated to no treatment and will be observed until Week 28 or the day when they return to a 50% reduction in EASI score (EASI50) and start the treatment in the extension trial.

Patients who discontinue the treatment but will continue on trial visits will be included in analyses with the available data. For patients who discontinue trial prematurely only available data will be used in the analyses.

For the final analysis of the trial to be performed once all patients have completed through the planned period, results will be summarized including the data from the reallocation period (Open-label Treatment phase). Results will be presented separately and in descriptive manner. The time windows for data presentation in this analysis are described in [Table 6.7: 1](#). In addition, analyses including the data from the double-blind period (initially used for the Primary Analysis) will be re-run after the final database lock.

To distinguish between assignment to trial periods/phases and AE assignments, please, refer to [Table 6.1:2](#).

Table 6.1: 2 AE assignment to analysis treatment groups

Randomised treatment	EASI75 response at Week 16	Open-label period	AE assignment to analysis treatment group
PLACEBO	Responder	No Treatment	AE that occurred between first randomised study drug intake and min[(EoS visit date), (last randomised study drug administration date + 112 days)] will be analysed under PLACEBO. AEs occurring later will be listed only.
PLACEBO	Non-Responder	BI 655130 Treatment	AE that occurred between first randomised study drug intake and Week 16 visit date (excluding) will be analysed under PLACEBO. AEs occurring later will be analysed under Open-label BI Treatment.
BI 655130	Responder	No Treatment	AE that occurred between first randomised study drug intake and min[(EoS visit date), (last randomised study drug administration date + 112 days)] will be analysed under BI 655130. AEs occurring later will be listed only.
BI 655130	Non-Responder	BI 655130 Treatment	AE that occurred between first randomised study drug intake and Week 16 visit date (excluding) will be analysed under BI 655130. AEs occurring later will be analysed under Open-label BI Treatment.

Treatment groups up to Week 16 will be labelled as follows:

- **"Speso 600 mg IV q4w"** (i.e., patients randomised to BI 655130 600 mg)
- **"Placebo"** (i.e., patients randomised to Placebo)
- **"Overall Total"** (across treatments: Placebo and BI 655130 600 mg), where appropriate.

Treatment groups for the efficacy analysis after week 16 will be labelled as follows:

- **"Open-label treatment: No Treatment"**
 - **"Placebo"** (i.e., patients randomised to Placebo in the double-blind treatment period and who did not receive an open-label BI 655130 treatment starting from Week 16 (V7))
 - **"Speso 600 mg IV q4w"** (i.e., patients randomised to BI 655130 in the double-blind treatment period and who did not receive an open-label BI 655130 treatment starting from Week 16 (V7))
 - **"Total"** (i.e., patients randomised either to Placebo or BI 655130 in the double-blind treatment period and who did not receive an open-label BI 655130 treatment starting from Week 16 (V7))
- **"Open-label treatment: Speso 600 mg IV q4w"**
 - **"Placebo"** (i.e., patients randomised to Placebo in the double-blind treatment period and received an open-label BI 655130 treatment starting from Week 16 (V7))
 - **"Speso 600 mg IV q4w"** (i.e., patients randomised to BI 655130 in the double-blind treatment period and received an open-label BI 655130 treatment starting from Week 16 (V7))
 - **"Total"** (i.e., patients randomised either to Placebo or BI 655130 in the double-blind treatment period and received an open-label BI 655130 treatment starting from Week 16 (V7))

Treatment groups for the safety analysis for the whole trial will be labelled as follows:

- **"Speso 600 mg IV q4w"** (i.e., patients randomised to BI 655130 600 mg)
- **"Placebo"** (i.e., patients randomised to Placebo)
- **"Total Speso 600 mg IV q4w OL"** (i.e., patients randomised either to Placebo or BI 655130 600mg and assigned to BI 655130 600 mg open-label treatment at Week 16)

More details on the technical implementation of these analyses are provided in the ADS Plan of this TSAP.

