18- For Responders (R) the EoS visit must be completed 16 weeks after last treatment, which is at the latest at Week 28 (V10). Responders (R) may complete EOS at any point after V7 (Week 16) if the patient drops to an EASI 50 score prior to the planned EOS. For Non Responder (NR) patients who have achieved EASI 50 and plan to participate in the extension trial, the EoS visit will be completed no earlier than Week 32. Non Responder patients not participating in the extension trial will complete a V11/FU1 visit between Week 32-44. If a patient should discontinue treatment prematurely every effort should be made to keep the patient in the trial and complete all of the remaining study visits or at a minimum an early EoS visit 16 weeks after last treatment.

[figure not shown]
19- At V1 (Screening) BSA will be assessed for eligibility. From V2 (baseline) onward BSA will be completed as part of SCORAD assessment.

20- Only Non-Responders not participating in the open label extension trial must complete an End of Study Safety Phone Call. V11 and End of Study Safety Phone call can occur on the same day only if the Residual Effect Period (16 weeks after last trial drug infusion) has been reached (WK44). The phone call cannot be performed before the V11.

21- Patients will be asked about their pregnancy status at the End of Study Safety Phone Call.

22- For Non-Responders participating in the open label extension trial, End of Study completion IRT call is registered at V11 as the End of Study Safety Phone Call is not required. For Non-Responders not participating in the open label extension trial, End of Study completion IRT call is registered only at End of Study Safety Phone Call (WK44). V11 is not registered in IRT.

TABLE OF CONTENTS

TITLE PAGE	1
CLINICAL TRIAL PROTOCOL SYNOPSIS	2
FLOW CHART	6
TABLE OF CONTENTS	10
ABBREVIATIONS	13
1. INTRODUCTION.....	16
1.1 MEDICAL BACKGROUND	16
1.2 DRUG PROFILE	17
1.2.1 Mode of Action	17
1.2.2 Nonclinical pharmacology.....	17
1.2.3 Clinical experience	18
1.3 RATIONALE FOR PERFORMING THE TRIAL	20
1.4 BENEFIT - RISK ASSESSMENT.....	20
2. TRIAL OBJECTIVES AND ENDPOINTS.....	22
2.1 MAIN OBJECTIVES, PRIMARY AND SECONDARY ENDPOINTS.....	22
2.1.1 Main objectives.....	22
2.1.2 Primary endpoint	22
2.1.3 Secondary endpoint(s)	22
	
3. DESCRIPTION OF DESIGN AND TRIAL POPULATION	24
3.1 OVERALL TRIAL DESIGN AND PLAN	24
3.2 DISCUSSION OF TRIAL DESIGN, INCLUDING THE CHOICE OF CONTROL GROUP(S)	25
3.3 SELECTION OF TRIAL POPULATION	25

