3.1 OVERALL TRIAL DESIGN AND PLAN

This is a double-blind, placebo-controlled study assessing the safety, tolerability and efficacy of 600 mg BI 655130 compared to placebo given intravenously every 4 weeks in patients with moderate to severe atopic dermatitis. Safety and tolerability will be evaluated based on AE data collected and physical examination at every visit. At W16 patients will be evaluated for response to treatment by the change in EASI score compared to baseline. Patients who have responded, defined as having attained at least 75% reduction in EASI score compared to baseline will no longer receive treatment and will be followed at W 20, 24 and 28 to evaluate the sustainability of their response. If this patient reaches a 50% reduction in EASI score compared to baseline prior to the planned EOS at Week 28, they will immediately perform EOS and will be given the opportunity to receive treatment in an open label extension trial.

Patients who have not responded, defined as attained less than 75% reduction in EASI score compared to baseline will receive 600 mg BI 655130 at W16, 20, 24 and 28. Patients re-allocated to treatment, who reach EOS will be offered participation in the extension trial if they meet the eligibility criteria.

After re-allocation at Week 16, a patient will know what treatment they are on but will remain blinded to the treatment received until Week 16.

Figure 3.1.1 Trial design

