3.2 DISCUSSION OF TRIAL DESIGN, INCLUDING THE CHOICE OF CONTROL GROUP(S)

The placebo control is required to control for investigator bias and/or beneficial effects of being in a clinical trial. The 2:1 randomization (active: placebo) is warranted in order to maximize the number of patients receiving active treatment and is being controlled for from a statistical standpoint. The rationale for switching responding patients to follow-up with no-treatment at Week 16 is to evaluate the duration of clinical response off treatment. In addition, patients who have not attained at least a 75% reduction in EASI score compared to baseline will have the opportunity to receive (or continue) active treatment.

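### Observed-case EASI and SCORAD means at Week 24, and chiefly Week 28, leave out responders who have already fallen to EASI50, so they overstate durability off drug

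*SAP*

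**What the plan says.** **Purpose.** Protocol 3.2: "The rationale for switching responding patients to follow-up with no-treatment at Week 16 is to evaluate the duration of clinical response off treatment". Protocol 3.1 says that these patients "will be followed at W 20, 24 and 28 to evaluate the sustainability of their response".

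**Exit.** Response is a reduction of at least 75% at Week 16 (Protocol 3.1; SAP 5). For a responder who then falls to a 50% reduction before Week 28, Protocol 3.1 says: "they will immediately perform EOS and will be given the opportunity to receive treatment in an open label extension trial". Footnote 1 to SAP Table 6.1: 1 ends observation at Week 28 or at the return to EASI50. Flow Chart footnote 18 is softer: "Responders (R) may complete EOS at any point after V7 (Week 16) if the patient drops to an EASI 50 score". Protocol 6.2.3 counts a responder who stays until EASI50 as having completed the re-allocation period.

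**Missing data.** Protocol 7.5 does not impute missing continuous values and relies on the mixed model. SAP 6.6.2 does the same where such a model applies. For binary endpoints, SAP 6.6.2 sets a missing visit to non-response unless both neighbouring visits are successes. SAP 6.1 adds: "For patients who discontinue trial prematurely only available data will be used in the analyses".

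**Analysis after Week 16.** SAP 6.1 defines off-drug efficacy groups for this period and says of its results: "Results will be presented separately and in descriptive manner". The continuous summaries in SAP 7 count non-missing observations. SAP 6.7 assigns each value to a visit by its date (Table 6.7: 2), while SAP 5 equates the responders' end-of-study visit with V10 (Week 28).

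**The concern.** The off-drug period exists to answer one question, and the event that answers it is also the event that ends observation. A Week 28 value exists only for patients who were above a 50% reduction at their earlier visits. A plain mean of available values is therefore taken over a group from which the worst courses have been removed, and it can look steady while responders are relapsing.

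The group is likely to be small, so one or two exits can move the mean visibly. Because Protocol 6.2.3 treats these exits as completion, a count of premature discontinuations need not reveal them. The off-drug tables are also split by randomised arm, and an arm that loses response faster would be trimmed more, which would blur any contrast between arms.

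**Working it through.** **1. The plan's own figure.** There is none for Weeks 20 to 28. The sample size in Protocol 7.7 (42, as 28 and 14) concerns Week 16 only.

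**2. Direction.** Let p be the share of Week 16 responders who left before a given visit. Then

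observed mean − mean of all responders = p × (mean of stayers − mean of leavers).

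Leavers went out because their EASI reduction was 50% or less, so if they stayed off drug their later values would usually lie below those of stayers, and the difference is positive whenever p > 0. For SCORAD the same direction needs the two scores to move together, which is an assumption because exit is triggered by EASI.

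**3. Which visits.** Table 6.7: 2 gives extended windows of Days 127–154 for Week 20, 155–182 for Week 24 and from 183 for Week 28. A patient who exits at the Week 20 visit (Day 141) still contributes that value to Week 20. So p is essentially zero at Week 20; only an exit at an unscheduled visit up to Day 126 would be lost from it. Weeks 24 and 28 are exposed to exits at earlier visits.

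**4. Number of responders (assumption).** With the protocol's SD of 30 and difference of 25, and assumed mean reductions of 55% and 30%, EASI75 rates are P(Z > 20/30) = 25.2% and P(Z > 45/30) = 6.7%. For 30 and 15 patients this gives 7.6 + 1.0, or about 9 responders. One exit is then 11% of the group.

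**5. Size (illustration; every rate of loss is an assumption).** Simulated Week 16 reductions were uniform from 75% to 100%. Each patient's loss per 4 weeks was normal with the mean and SD shown, with negative values set to zero. Visit noise had SD 8. Patients left at the first scheduled visit with a reduction of 50% or less, and that value was kept at that visit. The column for all responders shows the mean had everyone stayed off drug under observation. Gaps were computed before rounding.

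| Loss, mean/SD | W24 still in | W24 observed | W24 all | W24 gap | W28 still in | W28 observed | W28 all | W28 gap | W28 exit value carried |
|---|---|---|---|---|---|---|---|---|---|
| 3/3 | 100% | 80.8 | 80.8 | 0.0 | 100% | 77.7 | 77.6 | 0.1 | 77.5 |
| 5/5 | 100% | 76.5 | 76.5 | 0.1 | 97% | 72.0 | 71.1 | 1.0 | 71.2 |
| 10/8 | 98% | 67.2 | 66.6 | 0.6 | 81% | 63.4 | 56.2 | 7.2 | 59.2 |
| 15/10 | 94% | 59.1 | 56.8 | 2.2 | 63% | 58.3 | 41.6 | 16.8 | 50.7 |
| 20/12 | 86% | 52.3 | 47.0 | 5.4 | 46% | 55.9 | 26.7 | 29.2 | 44.8 |

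The Week 20 gap is 0.0 in all five rows.

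Check of the 10/8 row with the formula in step 2: p = 0.19 and the gap is 7.2, so leavers average 63.4 − 7.2/0.19 = 25.5 at Week 28. In the 15/10 row the observed mean barely moves from Week 24 to Week 28 (59.1 to 58.3), while the mean of all responders falls from 56.8 to 41.6.

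**6. What carry-forward recovers.** In the 10/8 row it brings 63.4 down to 59.2 against 56.2. It removes 4.2 of the 7.2 points and leaves 3.0, because leavers would have gone on worsening.

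**7. Binary endpoints.** In the same row, EASI75 at Week 28 is 30% among patients observed and 24% with non-response imputation. The planned rule keeps leavers in the denominator as failures.

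**The case against.** The best defence has five parts.

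- **The available-data sentence does not govern these patients.** It concerns premature discontinuation, and Protocol 6.2.3 counts an EASI50 exit as completion. This stands. The point rests instead on the exit rule, the absence of imputation in Protocol 7.5 and the descriptive analysis.
- **Exit is at 50%, response is 75%.** A reader might infer that the later means describe mainly patients who still respond. They do not: patients between 50% and 75% stay in and are counted. In the 10/8 scenario only 30% of those observed at Week 28 meet EASI75. A reader might also infer that Week 20 is biased or that relapses vanish altogether. Under the date windows neither follows, because the exit value is used once, in its own window.
- **Redaction.** Parts of the SAP's endpoint, missing-data and analysis sections are blacked out, and the visible secondary efficacy endpoints stop at Week 16. A time-to-loss analysis or an exit rule could sit there, so its absence cannot be asserted.
- **Protection already planned.** Binary endpoints are covered. Summaries show the number of non-missing values and individual values are listed, so a falling count is visible. The reason for the fall is not, and the mean stays too high. A mixed model could reduce the bias, since exit follows a recorded EASI, but the mixed models visible in SAP 7.4.1 and 7.5.2.1 target Weeks 4 and 16.
- **Low stakes.** SAP 7 calls all efficacy analyses exploratory, and no visible decision rule uses these means. That limits the weight of the point. Durability off drug is still the stated reason for the period.

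**Conclusion.** The concern holds for the continuous summaries at Week 24 and chiefly at Week 28. If any responder leaves at EASI50 before a visit, the observed-case mean at that visit is expected to be too favourable. The direction follows from the plan's own rules, given that leavers would not recover off drug and, for SCORAD, that the score tracks EASI.

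The size cannot be derived from the documents. Under the assumed rates of loss it is 0.0 to 5.4 percentage points of EASI reduction at Week 24 and 0.1 to 29.2 at Week 28. It would be smaller if the permissive wording of Flow Chart footnote 18 means that some patients stay in follow-up after reaching EASI50.

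One ambiguity could shift the bias. If early end-of-study values were tabulated under V10, as SAP 5 may be read, Weeks 20 and 24 would lose their low values and Week 28 would mix in values from earlier dates. The Week 16 primary analysis is not affected. This is worth correcting, but it is not a threat to the trial's main result.

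**What to change.** For Week 16 responders, keep the observed-case table and add:

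1. By visit and randomised arm: the number of Week 16 responders, the number still in follow-up, and the number who left at EASI50.
2. A by-visit EASI and SCORAD summary that carries the exit-visit value to later planned visits, labelled as removing only part of the bias.
3. A Kaplan-Meier curve of time from Week 16 to a 50% reduction, with numbers at risk, unless a redacted section already provides it. This answers the duration question most directly.
4. A sentence stating that an early end-of-study value belongs to the window of its date (SAP 6.7) and not to V10/Week 28 (SAP 5).

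Protocol 3.1 and Flow Chart footnote 18 should also be reconciled on whether the exit is immediate or optional, so that the curve has a defined event.

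The cost is a few tables, one figure and one sentence, all from data already collected. Trial conduct and the primary analysis do not change. The small downside is that carry-forward is a convention, which is why the observed cases stay beside it.

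### AE follow-up under the randomised arm depends on EASI75 response, with no equal-window drug-related AE or SAE table named; separately, SAP 7.8 applies SAF-OL to patients whom that set excludes

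*SAP*

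**What the plan says.** SAP 6.1 introduces Table 6.1: 2 with the words "To distinguish between assignment to trial periods/phases and AE assignments", so AE assignment follows that table and not the trial phases of Table 6.1: 1.

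- **Responders, both arms:** the randomised arm takes any "AE that occurred between first randomised study drug intake and min[(EoS visit date), (last randomised study drug administration date + 112 days". Later events are only listed.
- **Non-responders:** "AE that occurred between first randomised study drug intake and Week 16 visit date (excluding) will be analysed under BI 655130", with a parallel row for placebo. Later events go to the open-label column.

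Table 6.1: 1 ends the blinded phase for every patient at "Week 16 visit date + 1 day" (that date excluded).

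SAP 7.8.1 bases AE analyses on numbers of patients, and says that they are done separately for the double-blind and re-allocation periods. It lists a separate table of drug-related AEs, identified there and in 7.5.2.2 as the secondary safety endpoint, and separate tables for SAEs and drug-related SAEs. SAP 7.8 adds two outputs cut at the Week 16 visit without the residual effect period: the overall AE table and the any-AE table by system organ class and preferred term.

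SAP 6.3 defines SAF-OL as treated patients who went on to receive study medication after re-allocation. SAP 7.8 uses SAF-OL for safety beyond Week 16 in patients who do not get open-label drug.

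**The concern.** The length of AE follow-up under the randomised arm is set by EASI75 response at Week 16, an efficacy outcome observed after randomisation. If the drug works, more active than placebo patients get the longer window, and a count of patients with at least one event rises with time at risk. The secondary safety endpoint could then differ between arms with no difference in event rate.

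The sponsor added equal-window outputs in SAP version 2.0, but the table that carries the endpoint is not among those named.

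The SAF-OL sentence is a separate defect: it names a patient group and an analysis set that have no member in common.

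**Working it through.** **Inputs.** Blinded doses are at Weeks 0, 4, 8 and 12 (SAP 6.1). Planned days are Day 85 for Week 12 and Day 113 for Week 16 (SAP Table 6.7: 1), and Day 141 for Week 20, Day 169 for Week 24 and Day 197 for the responder end of study (Table 6.7: 2). The residual effect period is 16 weeks = 112 days (protocol 7.3.4). Planned numbers are 30 active and 15 placebo (protocol synopsis).

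**Step 1: the windows.** Last blinded dose plus residual period: 85 + 112 = 197, which reproduces the planned responder end-of-study day. So min(197, 197) = Day 197. For non-responders Day 113 is excluded, so the last counted day is 112. The ratio is 197/112 = 1.76. With the ±3-day visit windows, the responder end falls between Day 194 and Day 200. Responders "will be observed until Week 28 or the day when they return to a 50% reduction in EASI score (EASI50", so some windows are shorter: an end of study at Week 20 or Week 24 gives 141/112 = 1.26 or 169/112 = 1.51.

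**Step 2: which tables have equal windows.**

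| Table | Week 16 version named in SAP 7.8? |
|---|---|
| Overall AE summary (covers AESIs) | Yes |
| Any AE by system organ class and preferred term | Yes |
| Drug-related AEs (secondary endpoint) | No |
| SAEs; drug-related SAEs | No |

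**Step 3: size.** The documents give no response or event rates, so this is an illustration. Let q be the proportion with an event by Week 16, w the average week at which responders' counting ends, k the hazard after Week 16 relative to before, and r the responder share. The hazard is the same in both arms.

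P(w) = 1 − (1 − q)^(1 + k(w − 16)/16)

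Artificial difference = (r_active − r_placebo) × (P(w) − q)

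With r = 40% v 10%, q = 10%, k = 1 and w = 28: P = 1 − 0.9^1.75 = 0.1684, and the difference is 0.30 × 0.0684 = 2.05 points (12.7% v 10.7%), or 0.62 of 30 patients. Other cases with r = 40% v 10%, in percentage points:

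| q | k | w = 20 | w = 22 | w = 28 |
|---|---|---|---|---|
| 10% | 1 | 0.70 | 1.05 | 2.05 |
| 10% | 0.5 | 0.35 | 0.53 | 1.05 |
| 5% | 1 | 0.36 | 0.54 | 1.08 |
| 25% | 1 | 1.56 | 2.30 | 4.37 |

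With q = 10%, k = 1 and w = 28, active responder shares of 20%, 30% and 60% against 10% on placebo give 0.68, 1.37 and 3.42 points. Equal shares give 0, and 10% active v 20% placebo gives −0.68. A high corner, q = 50% with 50% v 10% responders and the day ratio 1.76, gives 8.2 points (0.082 × 30 = 2.5 patients). A rate that high is nearer to all AEs, which already have a Week 16 table. For scale, one patient is 100/30 = 3.3 points on active and 100/15 = 6.7 on placebo.

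**Step 4: SAF-OL.** SAP 6.3 requires study medication after re-allocation. SAP 7.8 selects patients without it. The overlap is empty.

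**The case against.** **The period split may already equalise the windows.** SAP 7.8.1 separates AE analyses into double-blind and re-allocation periods, and Table 6.1: 1 closes the blinded phase at the same point for everyone. On that reading the drug-related and SAE tables already have equal windows. This is a fair reading but not a settled one. SAP 6.1 refers AE assignment to Table 6.1: 2, and SAP 7.8 describes its Week 16 outputs as additional and without the residual effect period, which implies that the main tables include it. What stands is that the documents are ambiguous.

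**The count may exist inside the overall table.** A reader might infer that no equal-window count of drug-related AEs or SAEs will be produced. The documents do not support that. The Week 16 overall table may carry such lines; its layout is left to sponsor guidance, and "More details on the technical implementation of these analyses are provided in the ADS Plan of this TSAP". Only the absence of a named table can be shown.

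**Each rule has a reason.** The responder tail is the residual effect period of protocol 7.3.4, and non-responders have to be cut because open-label drug starts at Week 16. This stands: neither rule is an error on its own. The imbalance comes from using both in one between-arm count.

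**The effect is small and does not hide harm.** If the drug works, the artefact adds events to the active arm. Safety is descriptive and no test is planned. This stands.

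**SAF-OL.** A reader might infer that patients without open-label drug have no analysis set at all. That goes too far: SAP 7.8 opens by basing all safety analyses on the SAF, which holds every treated randomised patient. One sentence is wrong, possibly through a stray word.

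**Conclusion.** The point holds as a minor one, in two parts.

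(a) Under Table 6.1: 2 the AE window is nominally Day 197 for responders and Day 112 for non-responders, and the documents do not make clear that the drug-related AE and SAE tables are produced on equal windows. The windows follow from the SAP's own planned days. The size rests on assumed rates: 0.7 to 2.1 points, or 0.2 to 0.6 of 30 active patients, at a 10% event rate with 40% v 10% responders and constant hazard. It is smaller if the hazard falls off drug, zero with equal response, and larger only with higher event rates or wider response gaps. It would not support a claim that the safety comparison as a whole is materially biased.

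(b) The SAF-OL sentence in SAP 7.8 contradicts SAP 6.3 and, as written, selects no patients. This part needs no assumption.

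Three further items are clarifications and do not carry the point:

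- Table 6.1: 2 has no row for a non-responder without open-label drug. Protocol Flow Chart footnote 3 makes early discontinuers non-responders, and the SAP keeps them: "Patients who discontinue the treatment but will continue on trial visits will be included in analyses with the available data".
- SAP 6.1 labels the open-label safety group as patients "assigned to BI 655130 600 mg open-label treatment at Week 16", whereas SAP 6.3 goes by receipt.
- The Week 16 visit day is inside the blinded phase but outside the non-responders' AE window. This may be intended, since open-label dosing starts that day.

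**What to change.** 1. Add to SAP 7.8 the drug-related AE table and the SAE and drug-related SAE tables, cut at Week 16 without the residual effect period, and use them for the between-arm comparison. Keep the residual-period tables of protocol 7.3.4 alongside.
2. State in SAP 7.8.1 whether the period split or Table 6.1: 2 governs each AE table.
3. Correct the SAF-OL sentence so that SAF-OL is used for patients who received open-label drug, and state that patients without it are analysed on the SAF after Week 16.
4. While editing, add a row to Table 6.1: 2 for non-responders without open-label drug, consistent with protocol 7.3.4. Use one of assigned or received throughout. Say whether the Week 16 visit day is in or out of the Week 16 outputs.

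The cost is a few extra AE tables and some SAP wording. Data collection does not change, and nothing conflicts with protocol 7.3.4. With one Week 16 cut for all patients the nominal window is Days 1 to 112 in both groups, and the difference due to window length alone is zero.
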